The activation status of T-cell populations may provide another indicator of cellular immunity potentially involved in pregnancy loss. The IL-2 receptor has been reported to be absent on T-cells in normal first trimester decidual tissues using immunohistochemical techniques [16]; however, using flow cytometry, CD3⁺CD25⁺ activated T-cells have been identified in decidual tissue [17]. CD69 is another early activation marker expressed on the surface of T-cells [18]. A proportion of T-cells constitutively expresses this marker throughout the menstrual cycle and in normal early pregnancy.

Approximately 60% of spontaneous abortions are attributable to numerically abnormal chromosomes in the developing conceptus [19], yet limited data to date addressing immunological phenomena in the decidua of miscarried women has compared their data relative to well-defined chromosomal abnormalities belonging to conceptuses. This is important since the chromosome abnormality trisomy 16, which occurs in 26% of all spontaneous abortions, is incompatible with life [20] and would thus be an undisputed cause of spontaneous abortion. Therefore, the purpose of our study was to determine whether decidual leukocyte subpopulations and their associated activation markers were different between women having miscarriage of either a trisomy 16 conceptus (47XY+16 or 47XX+16) compared with a chromosomally normal male conceptus (46XY) and compared with gestationally age-matched decidual tissues. Samples from presumably normal female conceptuses (46XX) were not chosen for study because of the inability to accurately differentiate from possible maternal cell contamination.

For managing with miscarriage or termination of pregnancy (TOP) in first trimester loss, ultrasound-guided manual vacuum aspiration (USG-MVA) is one of the treatment options. USG-MVA for the treatment of early pregnancy loss has been used for many decades. It had been reported that USG-MVA is safer, more cost-effective, and is associated with shorter hospitalization time and cost than surgical evacuation under general anesthesia [21, 22]. USG-MVA is a surgical technique of suction curettage. It is performed by using a hand held vacuum source (a syringe with barrel and plunger) attached to a uterine cannula [23, 24] The USG-MVA device works by aspirating the uterine content via the cannula into the syringe. Furthermore, product of conception derived from USG-MVA can be sent for karyotyping analysis.

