B. Study objectives and hypotheses

I. Objective

- (1) To investigate the immune cells profile in decidua derived from early pregnancy loss and correlate the result to the embryo karyotyping.
- (2) To investigate the genetic abnormality spectrum of early pregnancy loss by comprehensive next-generation-sequencing based approaches.

II. Hypotheses

- (1) Decidua tissue is different between euploidy pregnancy and aneuploidy pregnancy.
- (2) Except for well-known genetic abnormalities, early pregnancy loss can be attributed to various genetic etiologies, including cryptic structural rearrangements, absence of heterozygosity (AOH), and single-nucleotide variant (SNV), which can be detected by sequencing approaches.

C. Subjects:

Women undergoing ultrasound-guided manual vacuum aspiration (USG-MVA) will be recruited at Obstetrics and Gynaecology in The Prince of Wales Hospital

I. Inclusion Criteria

- (1) Women 18 years old or above
- (2) Women with miscarriage or TOP who are suitable candidates for MVA
 - first trimester miscarriage or TOP
 - No fetal heart beat or TOP in those with CRL 25mm
 - incomplete miscarriage or TOP with POG <5cm
 - hemodynamically stable,
 - tolerates well with speculum examination

II. Exclusion Criteria

(1) Women who are not feasible for the MVA procedure

- cervical stenosis
- fibroid uterus >12 weeks in size
- known uterine malformation
- bleeding disorder
- clinically sepsis
- inability to tolerate pelvic examination

(2) History of psychological/ psychiatric problem

(3) Patient refusal

D. Sample Size

There are two groups in this study: (1) women who miscarry or TOP with chromosomally normal fetus; (2) women who miscarry or TOP with chromosomally abnormal fetus.

There is no literature data on the difference in leucocytes profile between groups. In calculating the sample size required, we are making an assumption that the degree to which other leucocytes are affected, is similar to that of CD45+ cell count.

According to our pilot result, the CD45+ cell count was 89.7 ± 18.3 in decidual samples from miscarried women with abnormal karyotyping and 102.3 ± 20.2 in miscarriage women with normal fetal karyotyping, respectively. The sample size required for an alpha value of 0.05 and 80% power would be 50 in each arm. Therefore, a total of 100 subjects will be recruited.

E. MVA procedure

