All women in both groups will receive identical standard routine care. They will fast after breakfast and be admitted to a day ward for the MVA procedure. USG-MVA will be carried out as a day procedure in an out-patient setting according to a pre-defined protocol. The patient will be given misoprostol 400µg orally for cervical priming 2-3 hours before the procedure. In case of heavy bleeding or passage of products of conception, pelvic examination and/or USG will be performed to ensure that USG-MVA is still indicated. Routine observations, including blood pressure, pulse and temperature are measured. An intravenous catheter (14G) will be inserted. All patients will be given 500mg naproxen orally 1 hour before the procedure. If the woman was allergic to non-steroidal anti-inflammatory drug, paracetamol or codeine will be used instead. The procedure will be carried out with a full bladder.

USG-MVA will be performed using a 60ml charged syringe (MedGyn Aspiration Kit IV, 02511, [name]) with a flexible curette (size 4 to 7 mm, subject to doctor's discretion) attached to it. An experienced doctor and a nurse will perform the procedure together. Transabdominal USG during MVA will be performed using Voluson E730 Expert US system. Before the procedure, paracervical block will be performed using a 23-gauge dental needle syringe to inject 5ml of 2% xylocaine into a depth of 0.5cm at the cervical-vaginal juncture at 4, 5,7, 8-o'clock position to reach the uterosacral ligaments and 5ml of local lidocaine gel (Xylocaine 2%) will be applied to the cervix a few minutes before the insertion of the MVA catheter. The MVA procedure will stop as soon as USG guidance confirmed that the uterine cavity is empty.

F. Blood collection

Patient's extra blood sample will be donated with consent if blood investigation is indicated by doctors. The amount of blood volume is approximately 5-10ml blood samples via the method of venipuncture by trained health workers. Identification of blood sample will be counter-checked with patient and sent to laboratory for immunity check.

G. Sample collection, separation, and preparation

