POCs obtained from MVA procedure were rinsed in normal saline thoroughly in the kidney basin to minimize maternal blood. Chorionic villi were considered as a proxy of fetal genetics, appeared to be yellowish in color and tree-projection-like in appearance, floating on the surface of the waterline. Decidua are originated from the mother, appeared substantive in structure and sank in the basin. The two different types of tissues are separated from each other for different testing.

- (1) Chorionic villi will be divided into two parts: one sent for histopathologic diagnosis as a standard clinical practice, while another aliquot for molecular analysis for a comprehensive genetic etiology investigation. Multiple-site chorionic villi sampling combined with low-pass genome sequencing (FetalSeq) will be performed for detecting site-to-site heterogeneity (the mosaicism phenomenon). For cases that remain genetically idiopathic, mate-pair sequencing (ChromoSeq) and 30x whole genome sequencing (WGS), more superior and high-resolution sequencing platforms will be performed for detecting cryptic structural rearrangements, absence of heterozygosity (AOH), and single-nucleotide variant (SNV).
- (2) The maternal decidua will be divided into two proportions: i) one proportion will be fixed in 4% formalin for 24 hours, routinely processed and embedded in paraffin wax; ii) another proportion will be rinsed immediately and then snap frozen-stored for further analysis if needed. 5 – 10 ml of blood will be taken for immunoassay.

H. Genetic studies on chorionic villi

For each POC sample, chorionic villi with good morphology were randomly biopsied with ophthalmic forceps under the microscope (Leica S6E stereomicroscope, Wetzlar, Germany), avoiding areas of severe blood contamination. All selected chorionic villi will be purified carefully in PBS. They will be finally collected in a 1.5 ml tube for DNA extraction. Genomic DNA (gDNA) will be extracted using a commercial kit DNeasy Blood & Tissue Kit (Qiagen, Hilden, Germany). Multiplex quantitative fluorescence polymerase chain reaction (QF-PCR) was performed on DNA for excluding maternal cell contamination (MCC) and polyploidy.

I. FetalSeq

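### The background rules out 46,XX conceptuses because of maternal contamination, Section D admits them, and Section H names no maternal DNA comparator that would tell the two apart

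*Protocol*

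**What the plan says.** **Background (before Section B).** The stated purpose is a comparison of decidual leukocytes between trisomy 16 losses, chromosomally normal male (46,XY) losses and tissue matched for gestational age. Normal 46,XX conceptuses "were not chosen for study because of the inability to accurately differentiate from possible maternal cell contamination".

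**Section D, Sample Size.** There are two groups, split by fetal chromosomes. The normal group is "1) women who miscarry or TOP with chromosomally normal fetus". There is no restriction by fetal sex, and no criterion in Section C adds one.

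**Section G.** Villi and decidua are separated in a basin by appearance. Villi are sampled at several sites for FetalSeq, and cases still unexplained go on to ChromoSeq and 30x whole genome sequencing. Part of the decidua is fixed; the rest is kept: "another proportion will be rinsed immediately and then snap frozen-stored for further analysis if needed". On blood the section says: "5 – 10 ml of blood will be taken for immunoassay".

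**Section F.** Blood is conditional: "Patient's extra blood sample will be donated with consent if blood investigation is indicated by doctors".

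**Section H.** Villi of good morphology are picked under a stereomicroscope, "avoiding areas of severe blood contamination", and purified in PBS. "They will be finally collected in a 1.5 ml tube for DNA extraction". Then: "Multiplex quantitative fluorescence polymerase chain reaction (QF-PCR) was performed on DNA for excluding maternal cell contamination (MCC) and polyploidy". No maternal sample is named as a reference for that test.

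**The concern.** The background identifies a specific problem: a normal female result may be the mother. It answers by not using such samples. The operative design uses them, and nothing later in the protocol says how the problem was solved.

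The named test does not fill the gap as described. QF-PCR on one DNA sample can reveal a mixture of mother and fetus through extra or skewed alleles. It cannot reveal a sample that is entirely maternal, because that is an unmixed diploid female profile, just like a true 46,XX conceptus. FetalSeq is a copy-number method and would ordinarily read the same sample as normal.

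The error runs one way, and both objectives are exposed:

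- **Objective 1.** A wholly maternal sample is filed as normal whatever the conceptus was. Decidua from some aneuploid pregnancies then sits in the normal group and pulls the contrast toward no difference.
- **Objective 2.** The case becomes a false negative for chromosomal abnormality. It then looks unexplained, so it qualifies for ChromoSeq and 30xWGS, where the mother's SNVs, AOH or rearrangements could be reported as fetal causes of loss.

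**Working it through.** **1. The two designs side by side**

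| | Background | Sections C and D |
|---|---|---|
| Abnormal group | trisomy 16 | any chromosomally abnormal fetus |
| Normal group | 46,XY only | any chromosomally normal fetus |
| Third group | gestational-age-matched tissue | none |
| 46,XX | not chosen | not excluded |

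The conflict covers the whole purpose statement, not only the 46,XX sentence.

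**2. Is a maternal reference named anywhere?** QF-PCR is run on DNA from the selected villi. Blood goes to immune testing and is not available for every woman. Decidua goes to fixation, freezing and the immunological work of Section I. No section compares maternal and villus genotypes.

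**3. The plan's own figure.** Section D gives CD45+ counts of 89.7 (SD 18.3) for abnormal and 102.3 (SD 20.2) for normal karyotype, alpha 0.05, 80% power and 50 per arm.

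- Difference: 102.3 − 89.7 = 12.6.
- Pooled SD: √((18.3² + 20.2²)/2) = 19.27.
- n per arm = 2 × (1.960 + 0.842)² × 19.27² / 12.6² = 37 (38 with the t distribution), two-sided.

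The stated 50 is not reproduced at 80% power. At 50 per arm, z = 12.6 / (19.27 × √(2/50)) = 3.27, and power = Φ(3.27 − 1.96) = 90.5%. That mismatch is a separate matter; here it only fixes the starting point at about 90%.

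**4. Effect of wholly maternal samples.** Let f be their share of the group labelled normal. The documents do not give f; 5–20% is assumed, with 30% added to show where 80% power is lost. Let q = 0.60 be the share of these that come from abnormal conceptuses, taken from the background's figure for spontaneous abortions. With m = f × q:

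- difference = 12.6 × (1 − m)
- variance of the labelled-normal arm = (1 − m) × 20.2² + m × 18.3² + m(1 − m) × 12.6²
- pooled SD = √((that variance + 18.3²)/2)

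| f | m | Difference | Pooled SD | Power at 50 per arm |
|---|---|---|---|---|
| 0 | 0 | 12.60 | 19.27 | 90.5% |
| 5% | 0.03 | 12.22 | 19.30 | 88.6% |
| 10% | 0.06 | 11.84 | 19.33 | 86.5% |
| 20% | 0.12 | 11.09 | 19.38 | 81.6% |
| 30% | 0.18 | 10.33 | 19.41 | 75.9% |

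With q = 0.4, power at f = 20% is 85.0%; with q = 0.8 it is 77.9%.

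**5. What a 46,XY-only normal group would hold.** Assume half of normal conceptuses are male.

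- If 50 normal and 50 abnormal cases are obtained, about 25 are 46,XY. SE = √(18.3²/50 + 20.2²/25) = 4.80, and power = Φ(12.6/4.80 − 1.96) = about 75%.
- If 100 women are enrolled and 60% are abnormal, there are 100 × 0.40 × 0.50 = 20. Reaching 50 would then take 50/(0.40 × 0.50) = 250 women.

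This group suits a sensitivity analysis, since a wholly maternal sample cannot be typed 46,XY. It is too small to replace the main comparison at the planned size.

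**The case against.** The strongest reply is that the protocol takes contamination seriously. Villi are chosen by morphology under a stereomicroscope and purified, not merely sorted by eye in a basin. Multiple-site sampling, if sites are assayed separately, would expose a maternal site lying beside a male or aneuploid one. Another part of the villi goes to histopathology, though on a different aliquot. A reader might infer that QF-PCR is the only safeguard; Sections G and H do not support that. These steps make a wholly maternal sample less likely. None of them verifies that the sequenced DNA is fetal.

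A reader might also infer that the laboratory uses no maternal profile. The protocol is silent on this, and a laboratory procedure may supply one. What the text supports is that no comparator is stated.

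The exclusion of 46,XX sits in a past-tense background paragraph describing a different comparison, which Section D does not adopt. That is fair, and it is why the whole paragraph needs reconciling. It does not remove the reason the paragraph gives, which applies equally to Section D's normal group.

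Finally, nothing in the documents supports any particular f, and the 60% figure does not cover terminations, which are also enrolled. Both points stand.

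**Conclusion.** The point holds as a conflict between the background and the operative design, together with an unstated maternal comparator in Section H. As written, the plan gives no way to separate a wholly maternal sample from a normal female conceptus, so such a sample would be counted as normal.

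A reader might infer that this undermines the power of the CD45+ comparison. The figures do not support that. For an assumed f of 5–20% and q of 0.60, the difference falls from 12.6 to 12.2–11.1 and power from about 90% to 89–82%, still above the planned 80%. It drops below 80% somewhere between f = 20% and 30%, or just under at 20% if q were 0.8. These results take the pilot means and SDs as true and apply a spontaneous-abortion figure to a mixed population.

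The more serious harm is mislabelling and wrong fetal attribution under objective 2. It cannot be quantified from the documents, and a larger sample would not cure it. The change is worth making because it is cheap, but the point does not show that the design fails.

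**What to change.** 1. **Background.** Rewrite the purpose statement to match Section D: which groups are compared, and whether 46,XX conceptuses are eligible and on what condition. Changing the 46,XX sentence alone would leave the trisomy 16 and 46,XY comparison in conflict with Section D.
2. **Section H.** For villus samples that read as chromosomally normal female, compare the QF-PCR profile with the same woman's blood where it was taken, or otherwise with stored decidua. Class samples showing no non-maternal alleles as uninformative, not normal, and do this before any ChromoSeq or 30xWGS. If the laboratory already makes this comparison, stating so and giving the classification rule is enough.
3. **Section J.** Repeat the hypothesis 1 comparison with the normal group limited to 46,XY, as a sensitivity analysis. With roughly 20–25 such cases, judge it by whether the estimate agrees with the main one, not by its p-value.

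**Cost.** One extra DNA extraction and QF-PCR for the affected cases, with no new procedure for the patient, plus one extra analysis. Some cases will become uninformative and reduce the normal group. A maternal reference cannot be assumed for every woman: blood is conditional, stored decidua may be used up (the bulk RNA-seq in Section I takes 350 mg of frozen tissue), and decidua separated in the basin may itself contain fetal tissue.

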The decidual sample will be transferred into 10 ml RPMI 1640 (Sigma Aldrich UK) and transported to a single laboratory facility, without delay. The decidual sample will be passed through a 70-µm nylon filter (BD Falcon™, BD Biosciences, UK) to remove it from RPMI and associated blood, blotted and accurately weighed. Samples will be standardised to approximately 300 mg of tissue whenever possible. Mechanical dissociation will be applied, using Gentle MACs™ C tubes (Milteny Biotech) and 10 ml fresh RPMI to efficiently release all cells, using a preset function (Program C for 30 s, Program B for 30 s) designed as suitable for decidual tissue. The free cell lysate will be then passed through a 40-µm nylon filter to isolate connective tissue elements above this size, pelleted at ×500 g, and re-suspended to a final volume of 1.5 ml in BD staining buffer (BD Biosciences, UK). Two-hundred microliters of resuspended cells will be then incubated with the antibody cocktails (CD56, CD16, CD57, CD14, CD38, CD3, CD4, CD8, CD69, HLA-DR, CD28, CD15, CD33, CD66b Fox-3, PD-1, Tim-3, CTAL-4, IL-10, IL17, TGF-β, etc.). In parallel, the red blood cells of peripheral blood will be lysed by RBC lysis buffer and stained with the antibody cocktails. The antibody cocktails will be standardised to a final volume of 100 µl with BD staining buffer. Flow cytometric evaluation will be followed using co-localisation of these specific antibodies by multicolour/multitube flow cytometry.

V. Single-cell capture, library preparation, and sequencing

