Frozen tissue (350 mg) of endometrium in 2-ml microcentrifuge tubes will be lysed by milling (MM301, RETSCH Mill) for 5 min at 27 cycles/s using 3-mm Tungsten Carbide Beads (#69997, QIAGEN) in 359 μ l of ED2S buffer [36 mM citric acid, 44 mM NaOH, 0.4% (w/v) sacosyl, 1.5 M guanidine isothiocyanate, 183 mM NaCl, and 48 mM 2-mercaptoethanol in phenol]. After lysis, the suspension will be centrifuged at 13,000g, 1 ml of the supernatant will be transferred into a new tube, and 298 μ l of PBSP [125 μ l of 30% (w/v) sodium dodecylsulfate, 66 mM tris-HCl (pH 7.5), 19.8 mM EDTA, 265 mM 2-mercaptoethanol (pH 8.0), and 175 μ l of PBS] will be added, followed by mixing, incubation at 60°C for 90 s, and cooling on ice for 90 s. Phase separation will be induced by adding 126 μ l of chloroform, vortexing, and spinning at 21,000g for 5 min at room temperature. Aqueous supernatant (650 μ l) will be transferred into a new tube, and 1300 μ l of VB2G [98.2% isopropanol, 7.2 mM MgCl₂, 2.4 mM CaCl₂, 1 M guanidinium thiocyanate (GITC), and 5.0 mM tris(2-carboxyethyl)phosphine (TCEP)] will be added, followed by sample loading to QIAGEN RNAEasy MiniElute spin columns using a vacuum manifold. After loading, columns will be washed twice with 970 μ l of buffer EWL (18 mM NaCl, 2.7 mM MgCl₂, 0.9 mM CaCl₂, 0.5% Triton X-100, 360 mM GITC, and 5 mM TCEP), once with 970 μ l of 100% (v/v) ethanol, and twice with 500 μ l of 80% (v/v) ethanol. Membranes will be dried by centrifugation at 17,000g for 5 min, and samples will be eluted in 20 μ l of 10 mM tris-HCl (pH 7.4) by centrifugation under the same conditions. Total RNA (100 ng) will be used to generate RNA-seq libraries using Illumina TruSeq stranded mRNA LT kit. Libraries will be denatured and sequenced on Illumina HiSeq 2500 sequencer to generate 101-bp paired-end reads. Bulk RNA-seq analysis will be performed using standard RNA-seq pipeline. Briefly, after quality control, reads will be aligned to human (hg38) genome reference using STAR aligner (STAR_2.5.1a), allowing no more than three mismatches. Counts for genes will be generated using the function `featureCounts` in the R/Bioconductor package "Rsubread," followed by TPM calculation.

VII. scRNA-seq data processing

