The Drop-seq and 10x sequencing data will be processed using the standard pipeline (Drop-seq core computational protocol V1.2, <http://mccarrolllab.com/dropseq/>) with minor modifications. For Drop-seq Read1, bases 1 to 12 will be tagged with cell-barcode "XC," and bases 13 to 20 will be tagged with UMI "XM." For 10x Read1, bases

1 to 16 will be tagged with cell barcode XC, and bases 17 to 26 will be tagged with UMI XM. Read2 will be trimmed at the 5' end to remove any adaptor sequence, and the 3' end will be trimmed to remove poly(A) sequences of length six or more and then aligned to human (hg38) genome reference using STAR aligner (STAR_2.5.1a), allowing no more than three mismatches. Gene expression matrix will be then generated using the "MIN_BC_READ_THRESHOLD=2" option to retain UMIs with two or more reads.

J. Statistical Analysis

Quantitative data will be expressed as mean \pm standard deviation (SD)/95% confidence interval (CI) if they follow a normal distribution, median \pm inter-quartile range for skewed distribution. The baseline characteristics of the three groups of patients will be compared using the Mann-Whitney test. Differences between groups will be assessed by Student's t-test, ANOVA and non-parametric test where appropriate. P value of <0.05 will be considered statistically significant. Statistical analysis will be performed using SPSS version 26.0.

K. Consents

All subjects will be given a detailed explanation and their permission will be obtained before they are recruited into the study. A written consent form will be signed by the participants. The participants can withdraw from the research without any repercussions.

L. Ethical considerations

(1) Ethical conduct of the study

Risks of blood sample collection will be minimized. Minor discomfort or worrisome may be implied to the patients if blood sample collection is needed. Supports will be given by research team.

The study will be conducted according to the principles of the Declaration of Helsinki and its most recent updates (7th revision, 2013). Investigator(s) will ensure that the study complies with all local, federal, or country regulatory requirements as applicable.

(2) Confidentiality

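### Decidual RNA-seq has no stated check for fetal cells, although the groups are defined by fetal karyotype, so fetal carry-over can appear as a decidual difference

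*Protocol*

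**What the plan says.** Section D of the protocol defines the groups by the conceptus: "1) women who miscarry or TOP with chromosomally normal fetus; (2) women who miscarry or TOP with chromosomally abnormal fetus". The first hypothesis in Section B is about the mother's tissue: "Decidua tissue is different between euploidy pregnancy and aneuploidy pregnancy".

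Both tissues come from the same aspirate. Section G rinses it and sorts it by colour, shape and floating or sinking. Of the maternal part it says: "Decidua are originated from the mother, appeared substantive in structure and sank in the basin". Section H then selects villi under a microscope, cleans them, and applies QF-PCR, which "was performed on DNA for excluding maternal cell contamination (MCC) and polyploidy". No counterpart is described for the decidual portion.

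The two RNA-seq pipelines are under Section I:

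- **Bulk (I.VI).** Tissue is milled whole. After a quality control whose content is not given, reads are aligned, and then "Counts for genes will be generated using the function" featureCounts, followed by TPM. This subsection calls the tissue endometrium, although Section I concerns decidua.
- **Single cell (I.VII).** Reads are tagged, trimmed and aligned. Then "Gene expression matrix will be then generated using the" option that keeps UMIs supported by at least two reads. No other filter is named.

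Section J adds no step on the origin of cells or RNA.

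**The concern.** Contamination is usually noise. Here the possible contaminant carries the variable that defines the groups. If villous or trophoblast tissue stays in the decidual portion, an abnormal-karyotype case contributes RNA from abnormal cells and a normal-karyotype case does not. Genes on the affected chromosome can then differ between groups with no difference in the mother's tissue. A larger sample does not remove this bias; it makes the false difference easier to declare significant.

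The protocol itself treats mixing of maternal and fetal material as a practical problem. Section H tests villi for it. The background section says that presumed 46XX conceptuses were not chosen "because of the inability to accurately differentiate from possible maternal cell contamination". The same sorting step yields both portions, but only one is tested. The one dissociation of decidua that is described, for flow cytometry in I.IV, aims "to efficiently release all cells, using a preset function" and filters by size, which would not take out fetal cells. Whether the single-cell suspension is prepared in the same way is not stated.

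At stake is whether a group difference in the RNA-seq part of Objective 1 can be read as maternal.

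**Working it through.** The plan gives no figure for carry-over, so there is none to reproduce. The size is worked out over a range of assumed values.

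**Inputs from the protocol**
- About 60% of spontaneous abortions have numerically abnormal chromosomes, and 26% have trisomy 16 (background section).
- 50 women per group (Section D) and significance at P < 0.05 (Section J).

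**Assumptions**
- A fraction f of the RNA in the decidual portion is fetal, equal in both groups.
- Baseline expression per gene is the same in fetal and decidual tissue.
- A trisomic chromosome gives 1.5 times the normal expression.
- There is no true maternal difference.
- All 50 per group are sequenced, and between-woman CV per gene is 10% or 20%.

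**Step 1: within one affected case.** Expression relative to normal is (1 − f) × 1 + f × 1.5 = 1 + 0.5f.

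**Step 2: averaged over the abnormal group.** That group mixes abnormalities, so the mean shift is 0.5f times the share w carrying the trisomy in question. For trisomy 16 on the protocol's figures, w = 26/60 = 0.433. These shares describe spontaneous abortions; the study also enrols terminations, so w could differ.

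**Step 3: chance of a false positive per gene.** SE = CV × √(2/50) = 0.2 × CV. With shift δ, the rejection rate is Φ(δ/SE − 1.96) + Φ(−δ/SE − 1.96). Example at f = 10%, CV 20%: δ = 0.5 × 0.10 × 0.433 = 0.0217, SE = 0.04 and δ/SE = 0.542, so the rate is Φ(−1.418) + Φ(−2.502) = 0.078 + 0.006 = 0.084.

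| f | Shift within an affected case | Mean shift, w = 26/60 | Rejection rate, CV 20% | Rejection rate, CV 10% |
|---|---|---|---|---|
| 0 | 0 | 0 | 5.0% | 5.0% |
| 1% | 0.5% | 0.2% | 5.0% | 5.1% |
| 5% | 2.5% | 1.1% | 5.8% | 8.4% |
| 10% | 5.0% | 2.2% | 8.4% | 19.2% |
| 20% | 10.0% | 4.3% | 19.2% | 58.2% |

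If every abnormal case shared one trisomy (w = 1), f = 10% would give a 5% shift and a rejection rate of 24% at CV 20%. The calculation ignores the small extra variance from mixing affected and unaffected cases.

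**Step 4: transcripts and cell shares that do not depend on dosage.** A transcript made only by trophoblast is proportional to f. With equal f and similar fetal tissue in both groups, the between-group ratio is f/f = 1. If f were 2% in one group and 4% in the other, the ratio would be 4/2 = 2. Cell shares behave likewise: equal f shifts both groups alike. These biases therefore need f to differ by group, and nothing in the protocol says whether it does.

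**The case against.** **The protocol leaves this open rather than getting it wrong.** I.VII stops at the raw matrix and names no clustering or cell annotation, and I.VI mentions quality control without detail. Maternal or fetal assignment could follow in an analysis plan that is not shown. This stands in part: the text does not rule the step out, and it would be wrong to say that the protocol declares every read maternal. But it specifies both pipelines down to aligner version and options, and states a contamination test for one tissue and not the other. That asymmetry is in this document.

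**Sorting already lowers f.** It does, by an amount nobody has measured. Near f = 1% the dosage effect is negligible.

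**Stronger readings that the documents do not support.**
- A reader might infer that carry-over will produce a difference, or that fetal RNA alone could confirm the first hypothesis. No value of f is given. Objective 1 also rests on immunohistochemistry, multiplex immunofluorescence, serum cytokines and flow cytometry, and its sample size is based on a CD45+ count.
- A reader might apply 1 + 0.5f to the whole abnormal group. It holds only within cases carrying that trisomy.
- A reader might suppose that dilution by fetal cells explains the pilot CD45+ gap of (102.3 − 89.7)/102.3 = 12.3%. That would need f to differ by about 12 percentage points between groups, and the pilot value is a count with no stated unit or denominator, not a cell share from RNA-seq.

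**Conclusion.** The concern holds for the RNA-seq part of Objective 1. The decidual portion is sorted by eye, contamination is tested only in the other tissue, and no check for fetal material is stated between reads and counts. Because the groups are fetal-karyotype groups, carry-over can appear as a decidual difference even when it is equal in both.

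The mechanism follows from the design; the size does not. Under the assumptions above, the mean shift for trisomy 16 genes is about 1.1% at f = 5% and 2.2% at f = 10%. At f = 10% that takes the per-gene false-positive rate from 5% to between 8.4% (CV 20%) and 19.2% (CV 10%). Trophoblast transcripts and cell shares are at risk only if f differs by group. This supports adding a check; it does not show that the comparison is already invalid.

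**What to change.** **I.VII (single cell).** Assign each cell as maternal or fetal from reads already planned: Y-linked transcripts when the conceptus is male, genotype clustering of cells otherwise. Run the Objective 1 comparison on maternal cells only, and report the fetal share by karyotype group.

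**I.VI (bulk).** Cells cannot be removed after lysis, so estimate the fetal share of each sample from Y-linked reads (male conceptuses) and trophoblast-specific transcripts (all). Report it by group. Repeat the group comparison as a sensitivity analysis, either excluding samples above a limit fixed before the RNA data are linked to karyotype or adjusting for the estimated share. Reconcile the tissue name, endometrium or decidua, at the same time.

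**Two options to avoid.** A fetal-allele fraction for bulk samples needs genotypes that are not assured: FetalSeq is about 0.25-fold, 30x WGS is kept for cases still unexplained, and maternal blood is taken only when clinically indicated. Removing genes on the abnormal chromosome is ill-defined when that chromosome varies from case to case.

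**Cost.** Analysis work only; fetal sex can be read from the planned villus sequencing. Some cells are lost, a few bulk samples drop out of the sensitivity analysis, and Y-based estimates cover male conceptuses only. If the fetal share proves trivial, the report documents it.
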